6.3 Medical History

Medical history will be listed and summarized descriptively with count and percentage by coded term and treatment group for the ITT population. Coded terms will be defined using a current version of the Medical Dictionary for Regulatory Activities (MedDRA).

6.4 Inclusion/Exclusion Criteria and Subject Eligibility

Subject eligibility, e.g., inclusion and exclusion criteria failures will be listed for all screened subjects.

6.5 Study Drug Exposure and Treatment Compliance

The extent of exposure to study drug will be presented by duration of treatment and will be summarized with descriptive statistics by treatment group. Duration of exposure (in days) will be defined as (last dose date – first dose date + 1).

Treatment compliance, e.g., based on difference between actual capsule consumption and the expected capsule consumption of subjects, will be summarized by treatment group for the ITT population. Percent study drug compliance for the overall treatment period is calculated as: $100 \times [(\text{total number of capsules consumed}) / (\text{planned number of capsules the subject should have consumed while still actively enrolled})]$. The total number of capsules consumed will be calculated from the total capsules dispensed minus unused capsules returned for each subject.

Study drug exposure and accountability will be presented in listings.

6.6 Concomitant Medications

The latest World Health Organization Drug Dictionary (WHO-DD) will be used to categorize verbatim descriptions of non-study medications into the Anatomic Therapeutic Chemistry (ATC) classification system. Each verbatim name will be classified by anatomical main group (ATC level 1), therapeutic subgroup (ATC level 2), pharmacological subgroup (ATC level 3), chemical subgroup (ATC level 4), preferred term, and trade name (if appropriate).

Concomitant medications are referred to non-study medications that have been used on or after receiving the first randomized study medication. Medications will be categorized into 3 types:

Pre-treatment medications: any non-study medications that started and stopped prior to receiving the first randomized study dose.

Prior concomitant medications: any non-study medications taken before the first randomized study dose date and continued beyond the first randomized study dose date.

New concomitant medications: any new non-study medications that started on or after receiving the first randomized study medication.

Counts and percentages of subjects receiving concomitant medications, prior concomitant medications, and new concomitant medications will be summarized by treatment group and ATC classification level 4 and preferred term for the ITT population. Additionally, concomitant medications used for management of blood pressure or diabetes, if any, will be summarized separately.

Pre-treatment medications will be provided in a listing.

6.7 Protocol Deviations

Protocol deviations may include deviations from informed consent, study procedure, study medication administration, study restrictions, etc. All protocol deviations will be reviewed by clinical and statistical personnel to identify major deviations (those anticipated to have an impact on efficacy or safety findings) prior to database lock and unblinding. The ICH guideline on protocol deviation classification will be followed. The major protocol deviations will be used as one of the criteria to determine the subject's eligibility for inclusion in the PP population. Major protocol deviations will be summarized by treatment group and deviation category for the ITT population. All protocol deviations will be presented in a listing.

7 STATISTICAL METHODS OF ANALYSIS

7.1 General Considerations

Efficacy data will be summarized “as-randomized,” meaning the subjects will be summarized under the treatment they were randomized to, regardless of what treatment was actually received. The PP population will be the primary analysis population for all efficacy analyses while the ITT population will be used to support efficacy analyses, if appropriate. The Safety Population will be the primary analysis population for all safety analyses.

Estimand and its estimator(s) and estimate(s) for primary and secondary efficacy endpoints will be defined, where inferential statistical comparison and hypothesis testing related to a treatment effect are of interest. When analyzing the efficacy endpoints, effort will be made to distinguish intercurrent events from non-informative withdrawals, as well as applying various sensitivity analyses to assess the robustness of the estimate(s) for the pre-specified estimands. Details on estimands, estimators, estimates, and intercurrent events are discussed in individual endpoint analysis section.

7.1.1 Statistical Notation and Presentation

For descriptive statistical summaries, the sample size (n), mean, standard deviation (SD), standard error (SE), median, minimum and maximum will be calculated for continuous variables. For categorical variables, frequency and percentage in each category will be provided. Inferential statistical analyses will be performed using either parametric method (e.g., assessing continuous variables) or non-parametric method (e.g., assessing categorical variables). All tabulations of analysis results will include summaries for the three treatment groups: VI-0521 PHEN 15 mg/TPM 92 mg, Phentermine 30mg and Placebo.

Minimum and maximum values will be rounded to the precision of the original value. Means and medians will be rounded to one decimal place greater than the precision of the original value. SDs, SEs, and 95% confidence intervals (CIs) will be rounded to two decimal places greater than the precision of the original value. Percentages for summarizing categorical data will be rounded to one decimal place. P-values, if needed, will be presented with 4 decimal places and values less than 0.0001 will be presented as <0.0001.

The by-subject listings, including data at scheduled and unscheduled visits, will be sorted by treatment group, subject number, and then by date/time of the records.

7.1.2 Hypothesis Testing

All hypothesis testing will be based on two-sided test at a significance level of 0.05. The primary hypothesis is that VI-0521 does not have deleterious effect on SBP as measured by mean 24-hr ABPM in overweight or obese subjects compared to placebo.

For non-inferiority tests, the null hypothesis (H_0) to be tested is that the upper bound of the two-sided 95% confidence interval for the between-treatment group difference (VI-0521 minus placebo or phentermine) in change from baseline in 24-hr mean SBP is equal to or more than 3 mmHg. The alternative hypothesis (H_a) is that the upper bound of the two-sided 95% confidence interval for the between-treatment comparison with placebo (or phentermine) is less than 3 mmHg. Thus:

$$H_0: \Delta_U \geq 3 \text{ mmHg}$$

$$H_a: \Delta_U < 3 \text{ mmHg}$$

For superiority tests, the null hypothesis (H_0) to be tested is that the upper bound of the two-sided 95% confidence interval for the between-treatment group difference (VI-0521 minus placebo or phentermine) in change from baseline in 24-hr mean SBP is equal to or more than 0 mmHg. The alternative hypothesis (H_a) is that the upper bound of the two-sided 95% confidence interval for the between-treatment comparison with placebo (or phentermine) is less than 0 mmHg. Thus:

$$H_0: \Delta_U \geq 0 \text{ mmHg}$$

$$H_a: \Delta_U < 0 \text{ mmHg}$$

7.1.2.1 Multiplicity Adjustment

This study is designed to maintain an overall study-wise type I error rate of $\alpha=0.05$. A hierarchical gatekeeping approach will be used to control the family-wise type 1 error of the primary and secondary endpoints. The order of the hypothesis testing will be:

- (1) The comparison between VI-0521 and placebo for non-inferiority,
- (2) The comparison between VI-0521 and phentermine for non-inferiority,
- (3) The comparison between VI-0521 and placebo for superiority, and
- (4) The comparison between VI-0521 and phentermine for superiority.

If the superiority of top-dose VI-0521 versus phentermine is achieved for the primary endpoint, the same testing order and hypothesis tests will be applied to the secondary endpoints: change from baseline to Week 8 in mean DBP as measured by 24-hr ABPM, and then mean change in SBP and DBP from baseline to Week 8 as measured in clinic, respectively.

In this hierarchical testing procedure, only when testing of a given hypothesis is successful, the subsequent hypothesis tests will be evaluated; otherwise, the subsequent hypothesis tests will be considered exploratory.

7.1.3 Baseline and Change from Baseline

In general, the baseline value for each variable is defined as the last non-missing observation obtained prior to the dispense of the first study drug. The actual first randomized dose date/time will be compared to the date/time of data collection to define the baseline for each parameter. In the case where the last non-missing measurement (except AE and concomitant medications) and the first dose coincide at the same time, or the same date if time of the measurement is not collected, that measurement will be considered as baseline value. The change from baseline value is defined as post-baseline value minus baseline value. The percent change from baseline value is defined as $(\text{post-baseline value} - \text{baseline value}) / \text{baseline value} \times 100$.

7.1.4 Handling of Ambulatory Blood Pressure Monitoring Data

For the 24-hr ABPM, blood pressure and heart rate will be measured every 20 minutes from 6:00 to 22:00 hours, and every 30 minutes from 22:01 to 5:59 hours for 24 consecutive hours. The baseline and post-baseline values for mean ABPM (SBP and DBP) will be calculated by taking the average of ABPM measurements over the given 24-hr time period.

For assessment of daytime and nighttime blood pressure, “night” will be defined as the mean of all systolic or diastolic blood pressure values recorded between 24:00 and 05:00 (inclusive) and “day” will be defined as the mean of all systolic or diastolic blood pressure values recorded between 07:30 and 21:30 (inclusive).

Mean hourly changes in blood pressure and heart rate will be calculated by taking the average of ABPM measurements available at each hour and calculating the change from baseline of the average. The measurements taken in the 60 minute duration prior to each hour will be used to get the average value. For example, the average of blood pressure measurements taken at 6:05, 6:25 and 6:45 will be defined as the mean blood pressure at 7:00.

7.1.5 Handling of Multiple Observations or Out of Window Observations

For efficacy data, if multiple assessments were recorded for the same protocol defined visit (e.g., same nominal visit but different time points or re-assayed), the later one or the re-assayed data will be used for data summary and analysis.

If a subject has a scheduled visit, the assessment obtained at the scheduled visit will be used for data summary and analysis. Otherwise, if no scheduled visit assessment exists but unscheduled visit assessments are available within the visit window, the data from the latest unscheduled visit will be used for statistical analysis.

Regarding the visit windows that will be applied to handle multiple observations and unscheduled visits, Table 7-1 shows the protocol-defined visit windows and the data analysis visit windows. Protocol-defined visit windows are usually more stringent to ensure study better adherence to study schedule; however, it could be too narrow for inclusion of unscheduled visits for data analysis. In order to include study data collected from any unscheduled visits, the analysis time windows will be widened for visit attribution. Note that data collected from an unscheduled visit that is out of the time window will not be included in data analysis, but will be provided in listings.

Table 7-1 Analysis Visit Window

Visit Number	Visit Name	Study Week	Target Study Day ^[1]	Protocol-Defined Time Window	Time Window to Attribute Unscheduled Visit to Analysis Visit
1	Screening	Week -4	-28	--	--
2A	Baseline/Randomization	Week 0	-1	+3 days	The last measurement prior to receiving the 1 st randomized dose

Visit Number	Visit Name	Study Week	Target Study Day ^[1]	Protocol-Defined Time Window	Time Window to Attribute Unscheduled Visit to Analysis Visit
2B	Baseline/Randomization	Week 0	1	--	--
3	End of Titration	Week 4	28	±3 days	-3 and +6
4A	End of Study or Early Termination	Week 8	56	±3 days	Week 7 to all visits before or on the last study dose date
4B	End of Study or Early Termination	Week 8	57	--	All visits after the last study dose date

[1] Study day 1 is defined as the date of the first dose for each subject.

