9.6.2 Management of Blood Pressure

Concomitant medications used for management of blood pressure, must be fixed in number, dose, and frequency for the duration of the study unless specific “rescue” criteria are met for blood pressure.

Rescue criteria are defined as:

- Blood pressure \geq 160/100 mmHg, or;
- Blood pressure \leq 100/60 mmHg, and subjects exhibiting symptoms associated with low blood pressure, concomitant antihypertensive medications should be withdrawn or doses should be reduced.

As this study has a short (8-week) duration, and as the first post-randomization evaluation occurs after 4 weeks of treatment (half way through the study), if rescue criteria for blood pressure are met at the Week 4 visit, sites should make all reasonable efforts to keep the subject on the study, to continue taking study drug, and to have them return within 1-2 weeks for re-evaluation of their blood pressure. If rescue criteria are still met at the repeat visit, then sites should complete the final ABPM evaluation and end of study procedures. Once the final ABPM evaluation and end of study procedures have been completed, rescue therapy should be initiated, and the subject discontinued from the study.

Adverse events that require initiation or modification of antihypertensive therapy are considered events of special interest and should be clearly documented and explained to enable narratives.

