4.3 Exploratory Endpoints

The exploratory endpoints of the study are:

- Mean hourly changes in SBP and DBP from baseline to Week 8, defined as the mean change from baseline at each hour;
- Change in mean daytime and nighttime SBP as measured by 24-hr ABPM from baseline to Week 8;

- Change from baseline to Week 8 in nighttime “dipping” of SBP, and the percentage of subjects with a normal SBP “dipping” pattern at Week 8. A normal “dipping” pattern of SBP will be defined as a reduction of mean nighttime SBP of $\geq 10\%$ relative to mean daytime SBP during the same 24-hr recording;
 - SBP dipping is calculated as: $100 \times [(\text{mean daytime SBP} - \text{mean nighttime SBP}) / \text{mean daytime SBP}]$
- Change from baseline to Week 8 in nighttime “dipping” of DBP, and the percentage of subjects with a normal DBP “dipping” pattern at Week 8. A normal “dipping” pattern of DBP will be defined as a reduction of mean nighttime DBP of $\geq 10\%$ relative to mean daytime SBP during the same 24-hr recording;
 - DBP dipping is calculated as: $100 \times [(\text{mean daytime DBP} - \text{mean nighttime DBP}) / \text{mean daytime DBP}]$
- Percentage of subjects meeting the following BP thresholds at baseline and Week 8 as measured by 24-hr ABPM;
 - SBP: ≥ 160 mmHg for 2 consecutive readings; ≥ 180 mmHg for 2 consecutive readings;
 - DBP: ≥ 100 mmHg for 2 consecutive readings; ≥ 110 mmHg for 2 consecutive readings;
- Percentage of subjects with the average of three successive BP meeting the following thresholds at baseline and each post-baseline visit as measured in clinic;
 - SBP: ≥ 160 mmHg; ≥ 180 mmHg; ≥ 20 mmHg increase from baseline;
 - DBP: ≥ 100 mmHg; ≥ 110 mmHg; ≥ 15 mmHg increase from baseline;
- Change from baseline to Week 8 in mean 24-hr heart rate, mean daytime heart rate, mean nighttime heart rate, and mean hourly heart rate;
- Percentage of subjects meeting the following heart rate thresholds at baseline and Week 8 as measured by 24-hr ABPM;
 - > 100 bpm for 2 consecutive readings; > 100 bpm for at least 1 hour; > 100 bpm for at least 2 hours; > 100 bpm for at least 3 hours; > 100 bpm for at least 4 hours; mean daytime heart rate > 100 bpm;
- Percentage of subjects meeting the following heart rate thresholds at baseline and each post-baseline visit as measured in clinic;
 - > 100 bpm;
 - ≥ 10 bpm increase from baseline; ≥ 20 bpm increase from baseline

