7.3.2 Clinical Laboratory Evaluations

All hematology, fasting blood chemistry, lipid panel, urinalysis and other lab results will be listed, including scheduled and unscheduled/repeat measurements (if any). Laboratory

assessments that are outside of normal ranges and/or with potential clinical significance will be considered an abnormal value and flagged in the listings.

Baseline values, values at post-baseline visits, and change from baseline values will be summarized descriptively for all laboratory parameters with numerical measures by treatment. Additionally, shift tables will be generated to summarize the normal and abnormal (abnormal high and abnormal low) status change from baseline to post-baseline visits. The frequency and percentage of subjects with laboratory results above or below the normal range and threshold limits at each scheduled assessment or any time during the treatment will be summarized by treatment group. All laboratory measurements that are collected from unscheduled visits will be mapped according to the visit window defined in [Section 7.1.5](#). Data from any unscheduled visits that are not be able to mapped to a scheduled visit will not be summarized in the by-visit descriptive tables, but will be included in the assessment when summarizing the worst case scenario, e.g., abnormality status.

Laboratory tests are shown in the table below.

Hematology	Fasting blood full chemistry	Pregnancy Testing

• hemoglobin• hematocrit• red blood cell count• total white blood cell count• white blood cell differential (neutrophils, lymphocytes, monocytes, eosinophils, and basophils)• platelet count	
• albumin• alkaline phosphatase• ALT• AST• blood urea nitrogen• serum calcium• serum chloride• serum sodium• bicarbonate• creatinine (and estimated creatinine clearance)• gamma-glutamyl transpeptidase (GGT)• glucose• lactate dehydrogenase• serum phosphorus• serum potassium• total and direct bilirubin• total protein• uric acid• total cholesterol• triglycerides• LDL-C• HDL-C• TSH (at screening only)• HbA1c	
• Urine pregnancy test (WOCBP)
		Urinalysis
		
• midstream urinalysis with reflex microscopic evaluation
		Urine Drug Screen (Screening Only)
		
• cannabinoids• amphetamines• cocaine• barbiturates• benzodiazepine• opiates
		Serology (Screening only)

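### Unscheduled clinic blood-pressure and heart-rate readings are mostly listed only: SAP Table 7-1 leaves 57-70% of on-treatment days in no window, and vital signs lack the worst-case rule that laboratory data have

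*SAP*

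**What the plan says.** **Windows.** SAP 7.1.5 sets the rule for unscheduled data. If a scheduled assessment exists, it is the one used: "If a subject has a scheduled visit, the assessment obtained at the scheduled visit will be used for data summary and analysis". An unscheduled assessment is used only when there is no scheduled one and it falls inside a window. Outside every window it goes to the listings: "Note that data collected from an unscheduled visit that is out of the time window will not be included in data analysis".

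The last column of Table 7-1, headed "Time Window to Attribute Unscheduled Visit to Analysis Visit", gives these post-baseline windows:
- Visit 3 (target Day 28): 3 days before to 6 days after.
- Visit 4A (target Day 56): "Week 7 to all visits before or on the last study dose date".
- Visit 4B: "All visits after the last study dose date".

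**Thresholds.** SAP 4.3 defines the clinic blood-pressure thresholds by visit: "Percentage of subjects with the average of three successive BP meeting the following thresholds at baseline and each post-baseline visit as measured in clinic". The clinic heart-rate thresholds have the same structure. SAP 7.2.3 summarises them descriptively, on the per-protocol population with observed data.

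**Vital signs.** SAP 7.3.3 gives descriptive summaries by visit on the Safety Population, without thresholds, plus a listing.

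**Laboratory data.** SAP 7.3.2 uses the same windows but adds an exception for unscheduled results that cannot be mapped. They stay out of the by-visit tables, "but will be included in the assessment when summarizing the worst case scenario, e.g., abnormality status".

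**Re-check.** Protocol 9.6.2 asks sites, when a subject meets the blood-pressure rescue criteria at Week 4, "to have them return within 1-2 weeks for re-evaluation of their blood pressure". This visit is not in the protocol's schedule of events (Appendix 1).

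**The concern.** The trial's primary hypothesis is that VI-0521 does not harm systolic pressure. The clinic thresholds (for example systolic pressure of at least 160 or 180 mmHg, a rise of at least 20 mmHg, or heart rate above 100 bpm) are there to show individual outliers. Unscheduled visits are a natural place for outliers to be recorded, yet the general window rule keeps most of those readings out of every blood-pressure and heart-rate table.

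The SAP already recognises this problem and solves it for laboratory tests, but does not extend the solution to the variables the trial is about. Early readings also bear on the comparison with phentermine: both documents' Table 1 shows phentermine at 30 mg from Week 1 while VI-0521 is stepped up over four weeks.

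At stake is the completeness of the descriptive outlier tables. The hypothesis tests are not affected.

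**Working it through.** The documents give no figure for window coverage, so there is none to reproduce. The check is a count of days.

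**Inputs.** Day 1 is the first dose, the Visit 3 target is Day 28 and the Visit 4A target is Day 56 (SAP Table 7-1). Visit 3 may fall within 3 days either side of target. The re-check comes 1-2 weeks later, taken as 7 to 14 days (Protocol 9.6.2). The start of Week 7 is not stated. Assumed values are Day 43 (first day of the seventh week), Day 49 (the convention that makes Week 4 Day 28) and Day 50 (after seven completed weeks).

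**Step 1: on-drug coverage, Days 1-56.** The Visit 3 window is Days 28 - 3 = 25 to 28 + 6 = 34, which is 10 days.

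| Week 7 starts | Visit 4A window | Days in a window | Days in none | Share in none |
|---|---|---|---|---|
| Day 43 | 14 days | 10 + 14 = 24 | 56 - 24 = 32 | 57.1% |
| Day 49 | 8 days | 10 + 8 = 18 | 56 - 18 = 38 | 67.9% |
| Day 50 | 7 days | 10 + 7 = 17 | 56 - 17 = 39 | 69.6% |

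Moving the last dose across the Visit 4A tolerance (Day 53 to Day 59) widens the range to 32/59 = 54.2% through 39/53 = 73.6%. Most on-treatment days lie outside every window under each reading.

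**Step 2: where the re-check falls.** With Visit 3 on Day 28, the re-check is on Days 35-42, outside every window whichever start day is used. Across Visit 3 on Days 25-31 (7 values) and delays of 7-14 days (8 values), there are 7 x 8 = 56 combinations:
- 6 fall by Day 34 (3 from Day 25, 2 from Day 26, 1 from Day 27). They are inside the Visit 3 window, where the scheduled Week 4 value takes precedence.
- 6 fall on Day 43 or later (3 from Day 31, 2 from Day 30, 1 from Day 29). These are in the Visit 4A window only if Week 7 starts on Day 43, and count only if there is no scheduled Visit 4A value.
- In no window: 56 - 6 = 50 if Week 7 starts on Day 49 or 50, and 50 - 6 = 44 if it starts on Day 43.

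**Step 3: one reading followed through the plan.** Take an unscheduled clinic reading of 165/95 mmHg on Day 14, with no change of therapy, in a subject who attends every scheduled visit. It meets the 160 mmHg threshold. Day 14 is in no window, so it is out of the SAP 4.3 threshold tables and the SAP 7.3.3 summaries. It does not exceed 180/110 mmHg, so the serious-adverse-event rule in Protocol 12.1.4 does not apply. It led to no antihypertensive change, so the special-interest summary in SAP 7.3.1 does not apply. Unless it is reported as an adverse event for another reason, such as symptoms (Protocol 12.1.3), it appears only in a listing. An out-of-range laboratory value on the same day would enter the worst-case summary.

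**The case against.** The case on the other side is substantial and limits the point.

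**The re-check is not always lost.** A reader might infer that it never reaches the threshold tables. Under Protocol 9.6.2, a subject who still meets rescue criteria at the repeat visit goes on to the final ABPM and end-of-study procedures. These include clinic vital signs at Visits 4A and 4B (Protocol 10.4). The Table 7-1 windows place unscheduled visits and do not exclude a nominal Early Termination visit. The triggering Week 4 reading is a scheduled Visit 3 value and normally counts. Persistent elevation is therefore normally represented. What can drop out is mainly a re-check that no longer meets rescue criteria, though it could still meet a rise-from-baseline threshold. One caveat remains: SAP 7.2.1 states the mapping of Early Termination data to Week 8 for ABPM only. For clinic pressure it has to be inferred from the visit name.

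**Early readings can count.** It is also tempting to say that nothing before Day 25 can enter. Early Termination visits, and readings after the last dose under Visit 4B, can fall on any day.

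**The gap is not the only mechanism.** The by-visit definition and the precedence of scheduled values would set aside completers' unscheduled readings even if the windows had no gaps. A by-visit percentage is also not a wrong estimate of an ever-crossed percentage, which the SAP does not claim to report.

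**Labelling matters.** For efficacy data, SAP 7.1.5 takes the later of several assessments under one nominal visit. A re-check entered as Week 4 would replace the triggering value.

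**Other routes exist.** These include the SAE rule above 180/110 mmHg, the special-interest adverse events, the comparison of rescue requirement (SAP 7.3.6), the ABPM thresholds and the full listings. The clinic thresholds are exploratory and descriptive.

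All of this stands. It does not remove the exclusion rule or its contrast with laboratory data.

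**Conclusion.** The point holds in a limited form. Between 57% and 70% of Days 1-56 lie outside every window, the spread coming from the undefined start of Week 7. Because the thresholds are also by visit, with scheduled values taking precedence, most unscheduled on-drug clinic readings enter no threshold or vital-signs summary. This includes a 9.6.2 re-check that is logged as unscheduled and not converted to Early Termination. Laboratory data are treated differently without a stated reason.

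The percentages count calendar days, not readings or subjects. The documents give no expected number of unscheduled visits or re-checks, so the effect on any reported percentage is unknown and could be small. A reader should not infer that 57-70% of high readings are lost.

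The conclusion assumes that SAP 7.1.5, a general rule, governs the clinic vital signs in 7.3.3, which does not cite it. It also assumes that Early Termination clinic pressure is analysed as Visit 4. No primary or secondary result and no sample size changes. This is a cheap improvement to the outlier reporting.

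**What to change.** 1. Keep the by-visit rows in SAP 4.3 and 7.2.3 as they are.
2. Add to SAP 7.3.3, on the Safety Population, a row for each clinic blood-pressure and heart-rate threshold in SAP 4.3, counting subjects who meet it at any time after first dose. Use all scheduled and unscheduled readings, and word the rule like the laboratory one in 7.3.2.
3. State in Table 7-1 the study day on which Week 7 starts.
4. Give the 9.6.2 re-check its own label in the analysis data, so that the rule favouring the later assessment cannot replace the triggering Week 4 value.

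The cost is SAP wording, a few table rows and one derivation flag. No new assessment is needed, and the clinical handling of the re-check is untouched. A conditional row in protocol Appendix 1 would also label the visit, but it would need a protocol amendment with IRB/IEC approval (Protocol 17.1), and the analysis label does the same job.

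The downside is that subjects seen more often have more chances to cross a threshold. If visit frequency differs between arms, the any-time rows will partly reflect that, so they should be read alongside the by-visit rows.
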